7.7 EXTENT OF EXPOSURE

Total treatment time (days and number of courses) will be calculated for each patient; off-drug periods due to non-compliance or toxicity prior to permanent discontinuation will be included as treatment time. In addition the total treatment time will be summed over all patients and transformed to patient years. Standard descriptive summaries, by treatment group, of these data will be provided for the treated set of patients.

A Kaplan-Meier plot showing the number of patients at risk (exposed) during the study treatment period will also be produced.

Further summaries will also be produced:

- Treatment time (days) broken down by each dose level (50 mg, 40 mg, 30 mg and 20 mg for afatinib; 150 mg, 100 mg and 50 mg for erlotinib).
- Number and proportion of patients on each dose level over time.
- Time to first dose reduction and duration (days) of off-drug periods prior to first dose reduction.
- Plot of proportion of patients with the first dose reduction over time

Summary of time to dose escalation will be produced only for afatinib treatment group.

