Protocol date: 15 Nov 2011	Trial number: 1200.125		Revision date: 24 June 2016
Main criteria for inclusion:	
 
• Diagnosis of advanced stage NSCLC considered to be squamous histology, including mixed histology, in the opinion of the investigator.
 
• Eligible for EGFR-directed therapy in 2nd line setting.
 
• Measurable disease according to RECIST 1.1.
 
• Eastern Cooperative Oncology Group (ECOG) score: 0 or 1.
 
• Availability of tumour tissue material for correlative studies. Archived tumour tissue is acceptable.
 
• Adequate organ function.
 
• No prior treatment with EGFR directed small molecules or antibodies.
 
		
Test products:	Afatinib (BIBW 2992)		
dose:	Starting dose 40 mg once daily. Escalation to 50 mg/day at beginning of Course 2 in patients meeting specified safety and compliance criteria. Dose reduction to 40 (if applicable), 30, and 20 mg/day in the presence of drug-related adverse events.		
mode of admin.:	Oral		
Comparator products:	Erlotinib		
dose:	Starting dose of 150 mg once daily. Dose reduction to 100 and 50 mg/day in the presence of known drug-related adverse events.		
mode of admin.:	Oral		
Duration of treatment:	Until patient experiences disease progression, according to RECIST 1.1.		

Proprietary confidential information.

© 2016 Boehringer Ingelheim International GmbH or one or more of its affiliated companies. All rights reserved.

This document may not - in full or in part - be passed on, reproduced, published or otherwise used without prior written permission.

Name of company: Boehringer Ingelheim		Tabulated Trial Protocol	
Name of finished product: Giotrif ® / Gilotrif ® , Afatinib			
Name of active ingredient: BIBW 2992			
Protocol date: 15 Nov 2011	Trial number: 1200.125		Revision date: 24 June 2016

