#### 4.1.4.1.1 Dose escalation for afatinib

The dose of afatinib administered may be escalated to 50 mg at the start of Course 2 if all of the following criteria are met during Course 1:

- Drug-related CTCAE grade  $\leq 1$  skin rash
- Absence of diarrhoea, mucositis, and/or any drug-related event (any grade) other than skin rash CTCAE  $\leq 1$
- Afatinib dose was not previously reduced due to any of the AEs depicted in the Dose reduction scheme [Table 4.1.4.1.2: 1](#)
- Compliant dosing of afatinib, as described in [Section 4.3](#)

Dose escalation is prohibited in any situation other than that prescribed above. The patient should remain on 50 mg unless dose reduction becomes necessary (see [Table 4.1.4.1.2: 1](#)).

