**Proprietary confidential information.**

© 2016 Boehringer Ingelheim International GmbH or one or more of its affiliated companies. All rights reserved.

This document may not - in full or in part - be passed on, reproduced, published or otherwise used without prior written permission.

Table 4.1.4.1.2: 1 Dose reduction scheme for afatinib

AE type and CTCAE Grade	Action	Dose reduction scheme

Events related to study drug:
 
 
• Diarrhoea Grade 2 persisting for 2 or more consecutive days (48 hours) despite adequate anti-diarrhoeal medication/hydration
 
• Nausea and/or Vomiting Grade 2 persisting for 7 or more consecutive days despite anti-emetic treatment/hydration
 
• Reduced renal function to <math>\geq</math> Grade 2 as measured by serum creatinine, proteinuria or decrease in glomerular filtration rate of more than 50% from baseline
 
• Any drug related AE Grade <math>\geq</math>3
 
	
Pause treatment until patient has recovered to Grade <math>\leq</math>1 or baseline.
 
Resume treatment at reduced dose according to schedule opposite.
 
If patient has not recovered to Grade <math>\leq</math>1 or baseline within 14 days study treatment must be permanently discontinued.
	
If patient was receiving 50 mg, resume treatment at a dose of 40 mg.
 
If patient was receiving 40 mg, resume treatment at a dose of 30 mg.
 
If patient was receiving 30 mg, resume treatment at a dose of 20 mg.
 
If patient was receiving 20 mg, discontinue afatinib.

Acute onset and/or unexplained worsening of pulmonary systems (dyspnea, cough, fever)
	
Pause afatinib while clinical assessment to exclude ILD is completed.
	
If ILD is ruled out as a cause of symptoms, grade symptoms and relatedness and report as AEs.
 
If AEs are not related, resume afatinib at current dose. If AEs are drug related, follow directions in row above.
 
If ILD is confirmed, discontinue afatinib

 Baseline is defined as the CTCAE Grade at the start of treatment

 In the event that the patient is deriving obvious clinical benefit according to the investigator's judgement, further treatment with afatinib will be decided in agreement between the sponsor and the investigator.

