## 5.2 SAFETY

### 5.2.1 Endpoints of safety

Safety of afatinib and erlotinib will be evaluated by intensity and incidence of adverse events, graded according to NCI CTCAE version 3.0 ([R04-0474](#)). Safety endpoints include:

- The overall incidence and intensity of adverse events
- Gastrointestinal events (vomiting, nausea, diarrhoea)
- Skin reactions (rash, acne)

Tolerability of afatinib and erlotinib will be assessed based on dosage reduction and discontinuation due to adverse events.

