7.8.1 Adverse events

The analyses of adverse events will be descriptive in nature. All analyses of AEs will be based on the number of patients with AEs and NOT on the number of AEs.

Furthermore, for analysis of AE attributes such as duration, severity, etc. multiple AE occurrence data on the CRF, will be collapsed into AE episodes provided that all of the following applies:

- The same MedDRA lowest level term was reported for the occurrences
- The occurrences were time-overlapping or time-adjacent (time-adjacency of 2 occurrences is given if the second occurrence started on the same day or on the day after the end of the first occurrence)

- Treatment did not change between the onset of the occurrences OR treatment changed between the onset of the occurrences, but no deterioration was observed for the later occurrence

AE episodes will be condensed into AE records provided that the episodes were reported with the same term on the respective MedDRA level and that the episodes are assigned to the same treatment. For further details on summarization of AE data, please refer to the guideline 'Handling and summarization of adverse event data for clinical trial reports and integrated summaries'. (7)

The analysis of adverse events will be based on the concept of treatment emergent adverse events (TEAE). That means that all adverse events occurring between first drug intake till 28 days after last drug intake will be assigned to the randomised treatment. All adverse events occurring before first drug intake will be assigned to 'screening' and all adverse events occurring after last drug intake + 28 days will be assigned to 'post-treatment' (for listings only). For details on the treatment definition, see [Section 6.1](#).

An overall summary of adverse events will be presented. This summary will include the first 5 categories from the list below and AEs by highest CTC grade.

The frequency of patients with adverse events will be summarised by highest CTC grade (grade 3, 4, 5 and all grades to allow both treatment groups to fit on one page), treatment, primary system organ class and preferred term. Separate tables will be provided for patients with each of the following AE categories:

- All AEs.
- Drug related AEs.
- AEs leading to dose reduction.
- AEs leading to treatment discontinuation.
- Serious AEs.
- Drug related serious AEs.
- AEs leading to death.
- AEs in Afatinib patients who dose escalate from 40 mg to 50 mg.

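### The planned dose-reduction outputs mix afatinib returns to the 40 mg starting dose with reductions below it, so their timing and AE breakdown are not like for like with erlotinib

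*SAP*

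**What the plan says.** Protocol section 5.2.1 makes dose reduction one of two tolerability measures for both drugs: "Tolerability of afatinib and erlotinib will be assessed based on dosage reduction and discontinuation due to adverse events".

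The two arms have different dose ladders.

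- **Afatinib.** The synopsis gives "Starting dose 40 mg once daily. Escalation to 50 mg/day at beginning of Course 2 in patients meeting specified safety and compliance criteria". Section 4.1.4.1.1 sets the conditions for that step. The synopsis then lists 40 mg among the reduction levels: "Dose reduction to 40 (if applicable), 30, and 20 mg/day in the presence of drug-related adverse events". The first step of the afatinib dose reduction scheme (Table 4.1.4.1.2: 1) is "If patient was receiving 50 mg, resume treatment at a dose of 40 mg".
- **Erlotinib.** The start is 150 mg, there is no escalation, and the only reduction levels are 100 and 50 mg (synopsis; Table 4.1.4.2.1: 1).

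SAP section 7.7 plans, by arm, "Time to first dose reduction and duration (days) of off-drug periods prior to first dose reduction", and a plot of the proportion with a first reduction over time. SAP section 7.8.1 plans a table of "AEs leading to dose reduction". That category is among the first five, so it also enters the overall AE summary. Neither section defines a dose reduction or gives a reference dose.

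Four planned outputs bear on the gap: treatment time at each dose level, patients on each dose level over time, time to escalation (afatinib only), and an AE table for escalated afatinib patients.

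**The concern.** An afatinib patient who meets the escalation criteria, goes to 50 mg and returns to 40 mg is recorded as dose-reduced without ever having been below the starting dose. No erlotinib patient can be recorded that way. Escalation requires a Course 1 with no diarrhoea, no mucositis and no drug-related event beyond rash of grade 1 or less, so the patients affected are those who tolerated 40 mg best at the outset.

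The effect on the outputs is one-sided. In the any-reduction count, step-back-only patients can add only to the afatinib arm. In the time-to-first-reduction summary and plot they add afatinib events. For an escalated patient who later goes below 40 mg, the first-reduction date is set at the earlier 50 to 40 mg step. In the AE table, events that led to a return to 40 mg sit with events that led to a dose below it.

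At stake is how one of two stated tolerability measures is read. No hypothesis test, alpha allocation or efficacy result depends on it.

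**Working it through.** **Step 1. Set the ladders side by side.**

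| | Start | Reduction steps | Steps ending below start |
|---|---|---|---|
| Afatinib | 40 mg | 50→40, 40→30, 30→20 | 2 of 3 |
| Erlotinib | 150 mg | 150→100, 100→50 | 2 of 2 |

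The SAP has no wording that overrides the protocol's use of the term, so 50→40 mg falls within a dose reduction as planned.

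**Step 2. What the planned outputs already give.** SAP section 7 includes N in its summary statistics, and section 7.7 breaks treatment time down by level. Afatinib reductions go one level at a time, and escalation is allowed only from 40 to 50 mg at Course 2. If N at a level counts patients with any time there, N at 30 mg is the number of afatinib patients ever taken below 40 mg, and N at 100 mg is the erlotinib equivalent.

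The correspondence is close but not exact. The protocol bars afatinib reductions for unrelated AEs (section 4.1.4.1.2), whereas an erlotinib dose may also be lowered because of interacting medication (section 4.2.2.1). The by-level summary does not give the time to the first below-start reduction, or the AEs behind it. The plot of patients per level over time does not give these either, because a patient at 40 mg after Course 2 may never have escalated or may have stepped back.

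**Step 3. Size.** The plan states no figure to reproduce, so this is an illustration. Let e be the share of afatinib patients escalated and r the share of those whose only reduction is 50→40 mg.

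Excess in the afatinib any-reduction proportion = e × r. For erlotinib it is 0.

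Inputs:
- Afatinib arm: 398 (synopsis).
- Nearest information on e: protocol section 4.1.3 reports diarrhoea of any grade in 96.7% of 30 patients starting at 40 mg in an earlier afatinib trial, that is 29 of 30. At most 1/30 = 3.3% would then pass the no-diarrhoea criterion. The exact 95% interval for 1/30 is about 0.1% to 17%.
- r is not in the documents. Assume 30% to 60%.

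| e | Basis | e × r, points | Patients of 398 |
|---|---|---|---|
| 3.3% | 1/30 | 1.0 to 2.0 | 4 to 8 |
| 10% | assumed | 3.0 to 6.0 | 12 to 24 |
| 17.2% | upper limit for 1/30 | 5.2 to 10.3 | 21 to 41 |
| 30% | assumed | 9.0 to 18.0 | 36 to 72 |

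For scale, with an assumed 25% reduced in each arm, the standard error of the difference is √(2 × 0.25 × 0.75 / 398) = 3.1 points.

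Two cautions apply to the 3.3%. The 30 patients had EGFR-mutated adenocarcinoma, a different population, and their diarrhoea was counted over all treatment, not Course 1 alone. The second point would make true eligibility higher. In the other direction, section 4.2.3.1 says diarrhoea generally starts within two weeks, and the criteria on mucositis, other drug-related events and compliance would lower eligibility further.

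**The case against.** The strongest objection is that a 50→40 mg step is real toxicity of the randomised regimen. Titration is part of the afatinib strategy (protocol section 3.1), and the step is triggered by the listed drug-related events, including any of grade 3 or higher. A measure restricted to below-start reductions would omit an afatinib patient reduced for grade 3 diarrhoea at 50 mg and count an erlotinib patient reduced for the same event. That is an asymmetry the other way. This stands, and it is why the any-reduction measure should be kept.

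A second objection is that the frequency is already available. It largely is, by Step 2. A reader might infer that the plan makes it impossible to know how often 40 mg itself had to be lowered; the by-level summary does not support that reading. The timing and AE breakdown remain missing.

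A third objection concerns size. A reader might infer a distortion of up to 18 points, well above the standard error. That needs 30% of patients to escalate, which is outside the interval from the only 40 mg diarrhoea data in the documents. It also needs 60% of those to step back and go no lower. The documents support neither rate. Because the AE analyses are descriptive, the comparison with a standard error carries little weight.

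Finally, a definition could exist in the technical TSAP or the AE summarisation guideline that the SAP cites. Neither was available. The SAP cites the technical TSAP for AE groupings, so a definition there is possible but not indicated.

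**Conclusion.** The point holds in a limited form. The time to first dose reduction, its plot and the AE table combine two kinds of afatinib event, only one of which has an erlotinib counterpart. No planned output gives the like-for-like timing or AE breakdown.

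The size cannot be known from the documents. It is about 1 to 2 percentage points (4 to 8 of 398 patients) if eligibility follows the cited 40 mg diarrhoea rate and 30% to 60% of escalated patients step back and go no lower. It is larger only if many patients escalate.

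The documents do not support a reading that the plan is biased against afatinib or that the any-reduction measure is wrong. That measure describes the regimen as given and answers a different question. Minor severity; a cheap improvement.

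**What to change.** - **SAP 7.7.** State that a dose reduction includes 50→40 mg. Keep the any-reduction summary and plot. Add, by arm, time to first reduction below the protocol starting dose (afatinib <40 mg, erlotinib <150 mg) to both.
- **SAP 7.8.1.** Keep the table of AEs that led to any reduction. Show separately the afatinib patients whose only reduction was 50→40 mg.
- Report the two measures side by side, neither replacing the other. No dosing rule changes.

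Cost: the dose levels and dates are already needed for SAP 7.7, so the timing part is a few extra rows and a second curve per arm. The AE part needs more work. Protocol section 5.2.2.2 has the investigator record the action taken for each AE, so separating the 50→40 mg steps means linking AEs to dose records. The report also needs a short explanation of why two reduction measures appear.

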7.8 SAFETY ANALYSIS

All safety analyses will be performed on the treated set.

7.8.1 Adverse events

The analyses of adverse events will be descriptive in nature. All analyses of AEs will be based on the number of patients with AEs and NOT on the number of AEs.

Furthermore, for analysis of AE attributes such as duration, severity, etc. multiple AE occurrence data on the CRF, will be collapsed into AE episodes provided that all of the following applies:

- The same MedDRA lowest level term was reported for the occurrences
- The occurrences were time-overlapping or time-adjacent (time-adjacency of 2 occurrences is given if the second occurrence started on the same day or on the day after the end of the first occurrence)

- Treatment did not change between the onset of the occurrences OR treatment changed between the onset of the occurrences, but no deterioration was observed for the later occurrence

AE episodes will be condensed into AE records provided that the episodes were reported with the same term on the respective MedDRA level and that the episodes are assigned to the same treatment. For further details on summarization of AE data, please refer to the guideline 'Handling and summarization of adverse event data for clinical trial reports and integrated summaries'. (7)

The analysis of adverse events will be based on the concept of treatment emergent adverse events (TEAE). That means that all adverse events occurring between first drug intake till 28 days after last drug intake will be assigned to the randomised treatment. All adverse events occurring before first drug intake will be assigned to 'screening' and all adverse events occurring after last drug intake + 28 days will be assigned to 'post-treatment' (for listings only). For details on the treatment definition, see [Section 6.1](#).

An overall summary of adverse events will be presented. This summary will include the first 5 categories from the list below and AEs by highest CTC grade.

The frequency of patients with adverse events will be summarised by highest CTC grade (grade 3, 4, 5 and all grades to allow both treatment groups to fit on one page), treatment, primary system organ class and preferred term. Separate tables will be provided for patients with each of the following AE categories:

- All AEs.
- Drug related AEs.
- AEs leading to dose reduction.
- AEs leading to treatment discontinuation.
- Serious AEs.
- Drug related serious AEs.
- AEs leading to death.
- AEs in Afatinib patients who dose escalate from 40 mg to 50 mg.

The system organ classes will be sorted according to the standard sort order specified by EMEA, preferred terms will be sorted by frequency (within system organ class).

In order to most accurately characterize those adverse events related to different mechanism, MedDRA SMQ and HLT (with some modification) will be used to group MedDRA PT for rash/acne, stomatitis, ocular effects, lip effects, nail effects and fatigue. As a first step in the analysis of grouped AE, all constituent PT will be presented in a separate table for each grouped AE. The first 5 standard tables will be supplemented with tables using the grouped AE. Groupings will follow the project standard and details are defined in the technical TSAP. In these tables the grouped AEs will replace the original PTs for all AEs that are included within the grouped term. The grouped AE categories will then be tabulated along with all remaining MedDRA PTs, sorted by descending frequency. A reference table presenting all project defined groupings and MedDRA PTs within each grouping will also be produced.

Additional tables will be produced to describe the frequency, intensity, time to onset, and clinical consequences for AE of special interest, diarrhea and rash/acne.

Separate listings will be prepared for patients who are identified as having experienced any of the following AE. For AE other than the single PT dehydration, identification will be based upon modified MedDRA SMQ and HLT groupings. If sufficient events occur within the trial, analyses similar to those for diarrhea and rash/acne may be performed.

- dehydration
- renal insufficiency
- hepatic impairment
- ILD-like events
- heart failure

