## 7. STATISTICAL METHODS AND DETERMINATION OF SAMPLE SIZE

### 7.1 STATISTICAL DESIGN - MODEL

This is a randomized, open-label Phase III trial to evaluate the efficacy and safety of afatinib versus erlotinib in patients with squamous cell NSCLC eligible to receive therapy in the second-line setting. Patients will be randomized to afatinib or erlotinib in a 1:1 ratio. Randomization will be stratified with respect to race (Eastern Asian vs. non-Eastern Asian).

An interim analysis will be performed as described in [Section 7.3.4](#).

Overall survival is the key secondary endpoint. OS will be tested only if the primary endpoint of PFS shows statistical significance ( $p < 0.05$ , two-sided).

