## 7.6 DETERMINATION OF SAMPLE SIZE

[Table 7.6: 1](#) shows the number of PFS events required for the primary analysis. The Table indicates that 372 PFS events would be expected to provide 90% power for the log-rank test,

Proprietary confidential information.

© 2016 Boehringer Ingelheim International GmbH or one or more of its affiliated companies. All rights reserved.

This document may not - in full or in part - be passed on, reproduced, published or otherwise used without prior written permission.

presuming a hazard ratio of 0.714 for afatinib relative to erlotinib (corresponding to median PFS times of 14 vs. 10 weeks, respectively). Data on file ([R10-6208](#)).

Table 7.6: 1 Number of PFS events required for 80% and 90% power

	80% Power	90% Power
Median PFS for afatinib	14 weeks	14 weeks
Median PFS for erlotinib	10 weeks	10 weeks
Hazard ratio of afatinib vs erlotinib	0.714	0.714
Number of events required for both groups 	278	372
Total Number of randomised patients	350	500

 log-rank test, alpha = 0.05, two-sided

 The number of required events was calculated using EAST-5 software excluding interim analysis, with patients randomised in a 1:1 ratio at a rate of 6 patients per week.

Table 7.6: 2 indicates that 632 deaths would be expected to provide 80% power for the log-rank test, presuming a hazard ratio of 0.800 for afatinib relative to erlotinib (corresponding to median survival times of 8.75 vs. 7.00 months, respectively).

Table 7.6: 2 Number of deaths required for 80% and 90% power

	80% Power	90% Power
Median OS for afatinib	8.75 months	8.75 months
Median OS for erlotinib	7.00 months	7.00 months
Hazard ratio of afatinib vs erlotinib	0.80	0.80
Number of events required for both groups 	632	845
Total Number of randomised patients	800	1040

 log-rank test, alpha = 0.05, two-sided

 The number of required events was calculated using EAST-5 software excluding interim analysis, with patients randomised in a 1:1 ratio at a rate of 36 patients per month.

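### Adverse events are tabulated only as crude patient percentages although the design assumes longer treatment on afatinib; for steady-risk events this alone can open a gap of up to about 7 points

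*SAP*

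**What the plan says.** - **Measure.** SAP 7.8.1: "All analyses of AEs will be based on the number of patients with AEs and NOT on the number of AEs". The adverse event analyses are descriptive. Under SAP 7, percentages are relative to the treatment group, here the treated set.
- **Window.** SAP 7.8.1 and Protocol 7.3.3 count events from first dose to 28 days after the last dose.
- **Treatment duration.** Protocol 3.1: daily dosing until progression, unacceptable toxicity or another reason for withdrawal.
- **Planned effect.** Protocol 7.6: a hazard ratio of 0.714, "corresponding to median PFS times of 14 vs. 10 weeks, respectively".
- **Exposure.** SAP 7.7: "In addition the total treatment time will be summed over all patients and transformed to patient years". A Kaplan-Meier exposure plot is also planned. Neither is linked to adverse events.
- **Time-related safety summaries.** SAP 7.8.1 fixes time-to-onset tables for diarrhoea and rash/acne, and allows similar ones for five further groups if events suffice. Further analyses of the influence of exposure and onset time appear at the end of Protocol 7.3.3 and in SAP 7.8.2 (laboratory data). They are to be done when needed, and no method is given.

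**The concern.** If afatinib delays progression as planned, its patients stay longer on drug and are watched longer for adverse events. A percentage of patients with an event rises with time watched. For events that accrue steadily, the drug that works longer would look more toxic at equal weekly risk, and a real weekly advantage could vanish from the table. Assessing safety in both arms is a stated secondary objective (Protocol 2.2.2), and readers will set these columns side by side. The trial is open-label, so a time-aware summary chosen after results are seen would look selective.

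**Working it through.** **1. The plan's own figure.** Inputs from Protocol 7.1 and 7.6: hazard ratio 10/14, two-sided alpha 0.05, 90% power, 1:1 allocation.
Events = 4 × (1.960 + 1.282)² / [ln(10/14)]² = 4 × 10.507 / 0.1132 = 371.2, so 372 as stated. At 80% power the formula gives 278, also as stated. The planning medians are therefore a sound basis.

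**2. Observation time.** Assume time on drug is exponential with the planned PFS medians.
- Weekly stopping rate μ: ln 2/10 = 0.0693 (erlotinib); ln 2/14 = 0.0495 (afatinib).
- Mean weeks on drug, 1/μ: 14.43 and 20.20.
- Add the 4-week tail: 18.43 and 24.20. Ratio 24.20/18.43 = 1.31.

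The 40% difference is in median time on drug; the fixed tail reduces it to 31% in mean observation.

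**3. Crude percentage at equal weekly risk.** The documents give no weekly risk, so it is varied. With constant hazard λ in both arms:

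P = 1 − exp(−4λ) × μ/(μ + λ)

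Example, λ = 0.03: erlotinib 1 − 0.8869 × 0.6979 = 38.1%; afatinib 1 − 0.8869 × 0.6227 = 44.8%. Gap 6.7 points.

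Solving λ for a given erlotinib percentage:

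| Erlotinib | λ per week | Afatinib | Gap (points) |
|---|---|---|---|
| 5% | 0.0028 | 6.5% | 1.5 |
| 10% | 0.0059 | 12.7% | 2.7 |
| 20% | 0.0130 | 24.7% | 4.7 |
| 30% | 0.0215 | 36.1% | 6.1 |
| 40% | 0.0322 | 46.8% | 6.8 |
| 50% | 0.0460 | 56.9% | 6.9 |
| 80% | 0.1337 | 84.2% | 4.2 |
| 90% | 0.2192 | 92.3% | 2.3 |

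The maximum is 6.9 points. The gap is at least 5 points only for erlotinib percentages of about 22% to 74% (λ about 1.4% to 10.7% per week). For scale, with 398 and 397 patients the 40% row has a standard error of √(0.468 × 0.532/398 + 0.40 × 0.60/397) = 3.5 points, so a 6.8-point gap is about 1.9 standard errors.

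**4. A real advantage hidden.** If afatinib's weekly hazard were 20% lower (0.8λ), the table would show 20.7% versus 20%, or 30.8% versus 30%.

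**5. Sensitivity.**
- Extra stopping common to both arms at 1%, 2% or 3% per week: the gap at a 50% erlotinib percentage falls from 6.9 to 5.7, 4.9 or 4.2 points.
- Risk confined to the first 4 weeks: gap 0, because everyone is observed at least that long. Confined to the first 8 weeks: under 1 point.

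**6. What an event rate does.** For steady risk it removes the gap. At λ = 0.03, mean time to first event or end of window is 12.70 and 14.92 weeks: 0.381/12.70 = 0.448/14.92 = 0.030, ratio 1.00.

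For early risk it creates one. Suppose a share r of patients in each arm has an event spread evenly over the first 2 weeks (mean onset 1 week). Crude percentages are correctly equal. Mean time at risk is r × 1 + (1 − r) × 18.43 or 24.20.
- r = 10%: 16.68 and 21.88 weeks; rate ratio 16.68/21.88 = 0.76.
- r = 90%: 2.74 and 3.32 weeks; rate ratio 2.74/3.32 = 0.83.

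That is a spurious 17% to 24% advantage for afatinib.

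**The case against.** Much of the other side's case stands and sets the limits of the point.

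- **Planned PFS is not time on drug.** Patients also stop for toxicity, withdrawal or non-compliance, and treatment follows the investigator's reading while PFS uses central review. The gap shrinks (step 5) but persists.
- **Some tables do not fit the steady-risk model.** Symptoms of progression are recorded as adverse events (Protocol 5.2.2.1), death is itself a PFS event, and an event leading to discontinuation ends exposure. Crude percentages for progression-linked events need not be inflated, so one cannot say that serious and fatal events are affected most.
- **A rate can mislead the other way** (step 6). The named safety endpoints include gastrointestinal and skin events, and Protocol 4.2.3.1 says diarrhoea generally begins within 2 weeks on afatinib. The crude bias runs against the sponsor's drug; a rate applied to early events would run in its favour.
- **Some handling exists.** It covers two event groups firmly and five conditionally. The closing exposure sentence of Protocol 7.3.3 may apply to all safety data, but it commits to no method.
- **Unseen sources.** SAP 7.8.1 defers to a summarisation guideline and a technical analysis plan that are not available here. That patient-years go unused is therefore a statement about the visible text.
- **Low formal stakes.** The analyses are descriptive and no test depends on them.

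A reader might also take the quoted sentence to forbid exposure adjustment. It does not: it contrasts patients with event counts, and first events per patient-year would comply with it.

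**Conclusion.** The point holds in a conditional form. Beyond two event groups, the visible plan commits to no time-aware summary of adverse events, while its own design hypothesis implies about 31% longer mean observation on afatinib. For events with equal, steady weekly risk the resulting gap is at most about 7 points. It is at least 5 points only in the 22% to 74% range, 1.5 to 2.7 points at 5% to 10%, and near zero for early-onset events. This rests on exponential time on drug with medians of 14 and 10 weeks, constant hazard, the 28-day tail, and no stopping other than at progression; relaxing the last assumption lowers the figures.

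Two stronger readings are tempting. One is that adverse event rows in general would be 5 to 7 points apart for equally safe drugs. The documents give no event rates to support that, and rare, very common and early events fall outside the range. The other is that rates per patient-year should carry the between-drug safety statements. With diarrhoea described as early in onset, the protocol's own text argues against that for overall and gastrointestinal tables.

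This is a worthwhile, inexpensive improvement to the SAP. It does not invalidate the planned tables.

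**What to change.** In SAP 7.8.1, keep every crude table and add:

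1. **Cumulative incidence of first event by arm at fixed times**, for example 4, 12 and 24 weeks from first dose, for any, grade 3 or higher, serious, fatal and discontinuation adverse events. Treat death as a competing event. State the rule for patients whose window ends for reasons other than an adverse event. Censoring them removes the exposure difference but assumes that ending is unrelated to later risk; counting it as a competing event leaves the difference in.
2. **A supportive column for serious and other later-onset events only:** patients with a first event divided by patient-years to first event or end of window, with rate ratio and 95% confidence interval.
3. **A stated limitation:** the rate assumes a roughly constant hazard. With equal risk confined to the first 2 weeks it would give a ratio of about 0.76 to 0.83 in favour of afatinib, so it is not used for overall, grade 3 or higher, or early gastrointestinal and skin events.

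The cost is SAP wording and modest programming. Onset and dosing dates are already collected, and no visit, sample size or treatment rule changes. The downside is a few more safety displays, each of which needs its assumption stated.
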